## 7.4 Table of Assessments

Visit	Screening/ Baseline	Randomisation	Treatment Visit 1	Visit 2 3 months ( $\pm 6$ weeks)	Visit 3 6 months ( $\pm 6$ weeks)	Visit 4 12 months ( $\pm 6$ weeks)	Visit 5  2 years ( $\pm 6$ weeks)	Visit 6 3 years ( $\pm 6$ weeks)	Visit 7 4 years ( $\pm 6$ weeks)	Visit 8 5 years ( $\pm 6$ weeks)	After Visit 8**
Informed consent	x										
Randomisation		x									
Fitness for surgery assessment	x										
PSA	x			x	x	x	x	x	x	x	x
Standard care referral pathway to regional uro-oncology centre	x										
MRI guided pre-op surgical planning			x								
RARP (standard/control or NeuroSAFE/intervention)			x								
Adverse events	x	x	x	x	x	x	x				
EQ-5D-5L – (P/C/E/T)*	x			x	x	x					
ICIQ – (P/C/E/T)*	x			x	x	x					
IIEF-5 – (P/C/E/T*)	x			x	x	x					
RAND36 – (P/C/E/T)*	x			x	x	x					
Additional Erectile Function (EF) questionnaire (P/C/E/T)*				x	x	x					
Additional Treatments Assessment				x	x	x	x	x	x	x	x
Health Resource Diaries data collection				x	x	x	x				
RAND36, IIEF, EQ-5D-5L, ICIQ and Additional EF questionnaire – (P/E/C/T)							x				
EPIC-26 questionnaire (P/E)*								x	x	x	x

\*P – Postal, E – Email, C – Clinic, T - telephone

\*\* after visit 8 data to be collected for a maximum frequency of annually

 Visits after 12 months dependent on future funding

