## 11.3 Health Economics Analysis

A cost-utility analysis of the NeuroSAFE RARP compared to standard RARP will be undertaken using accepted methods. We will analyse cost-effectiveness using a short-run time horizon of 12 months and 2 years (within the trial period - all participants will be followed for at least 2 years). Costs will be assessed from the perspective of the NHS and PSS. Cost components included in the analysis will be the cost of the intervention (standard RARP and NeuroSAFE RARP); NHS costs (inpatient and outpatient visits, diagnostic tests, medications). Resource use data will be collected retrospectively from patients using questionnaires (resource use diary) at 3 months, 6 months 12 months and 2 years. Unit costs will be taken from standard sources.

The cost-effectiveness measures in the short-term model will be the incremental cost per unit of change in the QALY gained. Costs will be measured as described. QALYs will be calculated based on the health-related quality of life (HRQoL) collected using EQ5D5L and RAND36 questionnaires. Patients' utility profiles will be constructed assuming a straight line between each patient's HRQoL scores at each follow-up point. The QALYs experienced from 3 months to 2 years will be calculated as the area underneath this profile. Cost-effectiveness will be calculated as the mean cost difference between NeuroSAFE RARP versus RARP divided by the mean difference in outcomes (QALYs) to give the incremental cost-effectiveness ratio (ICER). A sensitivity analysis will be performed to control for input parameters uncertainty.

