2.1 Purpose of statistical analysis plan

This Statistical Analysis Plan (SAP) reports the details of the main effectiveness analyses of the NeuroSAFE randomised controlled trial.

Its purpose is to reduce bias in the analysis and presentation of study results by pre-specification of the analyses conducted and the statistical methods used, with an appropriate level of detail.

This SAP does not prevent adjustments to the statistical methodology during data analysis, provided that these adjustments are limited and justified. It also does not prevent conducting further secondary analyses that appear relevant after conducting the pre-specified analyses, these will also be limited, justified, and clearly identified.

This SAP covers only the main effectiveness (clinical) analysis of the trial up to the visit 4 follow-up (12 months). Longer term outcomes, quality of life and health economic evaluation will be covered in separate analysis plans.

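### Protocol 11.3 defines the ICER without baseline-utility adjustment or any measure of patient-level sampling error; the economic plan should add both

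*Protocol*

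**What the plan says.** Protocol 11.3 opens with a general promise: "A cost-utility analysis of the NeuroSAFE RARP compared to standard RARP will be undertaken using accepted methods". The estimator follows: "Cost-effectiveness will be calculated as the mean cost difference between NeuroSAFE RARP versus RARP divided by the mean difference in outcomes (QALYs". No covariate, regression model, confidence interval, bootstrap or net-benefit measure is named. The one uncertainty step is this: "A sensitivity analysis will be performed to control for input parameters uncertainty".

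On the QALY itself, 11.3 joins each man's scores by straight lines and then states: "The QALYs experienced from 3 months to 2 years will be calculated as the area underneath this profile". On horizon it says: "We will analyse cost-effectiveness using a short-run time horizon of 12 months and 2 years". It adds that "all participants will be followed for at least 2 years", whereas the footnote to the 2-year visit in Protocol 7.4 reads: "Visits after 12 months dependent on future funding".

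Protocol 7.4 schedules EQ-5D-5L and RAND36 at baseline, so a baseline utility is available for every man who completes them. SAP 1.5 stratifies randomisation by site only. SAP 4.7 and 4.8 adjust the clinical outcomes for site, age and the baseline value of the outcome.

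SAP 1.2.2 places the economic objective outside its scope, and SAP 2.1 says: "Longer term outcomes, quality of life and health economic evaluation will be covered in separate analysis plans". That plan is not among the documents.

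**The concern.** The cost-effectiveness answer is a ratio. If its denominator is small, modest noise in the QALY difference moves the ratio a long way, and a bare point estimate does not show this. Two steps would help, and 11.3 mentions neither.

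- **Baseline utility.** Allocation is not balanced on it, so the arms can differ by chance. Men who start higher tend to stay higher, so part of that difference reappears in the QALYs. The trial collects the variable needed to remove it and already does the equivalent for its clinical outcomes.
- **Sampling error.** Varying input parameters such as unit costs does not, by itself, show how far the joint cost and QALY result could move with a different sample of men.

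What is at stake is precision and honest reporting of uncertainty in a secondary outcome. The validity of the clinical comparison is not in question.

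**Working it through.** The documents state no cost, utility, QALY or ICER figure, so there is nothing to reproduce. What follows sizes the gap under stated assumptions.

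**Inputs**
- Men per arm: 364 evaluable / 2 = 182 (SAP 1.4).
- SD of utility, baseline and follow-up: 0.10 to 0.15, taken as equal (assumption).
- Correlation r between baseline and later utility: 0.4 to 0.6 (assumption). The same r is used for the QALY area, which is a simplification.

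**How baseline enters.** As written, the area starts at 3 months, so the baseline score is not part of it. Imbalance reaches the QALY difference only through correlation with later scores. The window also matches neither the 12-month nor the full 2-year horizon, so the shift is given per year of window.

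**Size of a chance imbalance.** SE of the baseline difference = SD × √(2/182) = SD × 0.1048.
- SD 0.10: 0.01048
- SD 0.15: 0.01572

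One SE is therefore 0.010 to 0.016 utility.

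**Carry-over into QALYs.** With equal SDs the slope of later on baseline utility equals r, so shift per year = r × imbalance.
- Lowest: 0.4 × 0.01048 = 0.0042
- Highest: 0.6 × 0.01572 = 0.0094

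That is about 0.004 to 0.009 QALY per year. Over 3 to 12 months (0.75 years) it is 0.003 to 0.007; over 3 to 24 months (1.75 years), 0.007 to 0.017. In relative terms, a one-SE baseline imbalance moves the QALY difference by r, or 0.4 to 0.6, of its own SE.

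**Precision gained by adjusting.** Variance ratio = 1 − r².
- r = 0.4: 0.84, a 16% cut; the SE is multiplied by 0.92
- r = 0.6: 0.64, a 36% cut; the SE is multiplied by 0.80

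This matches enlarging the sample by a factor of 1/0.84 = 1.19 to 1/0.64 = 1.56 for the QALY comparison.

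**Why an interval is needed.** Assume a QALY SD of 0.15 to 0.25, so the SE of the difference is 0.0157 to 0.0262. The chance that sampling error alone makes the estimated QALY difference negative is Φ(−true gain / SE): about 10% to 22% for a true gain of 0.02, and about 0.5% to 6% for 0.04. These gains are assumed; the documents give none.

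**The case against.** The strongest objection is that 11.3 is a protocol summary. It promises accepted methods, and SAP 2.1 announces a separate economic plan that could specify both steps. That stands in part: absence from 11.3 does not show absence from the plan. But an unseen plan and a general phrase are not pre-specification, and the remedy can simply go into that plan.

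A reader might infer more than the documents support:

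- **That the protocol prescribes an unadjusted analysis.** It does not use that word. SAP 4.7 also calls its target a difference in means and then estimates it with covariates. The text is silent on adjustment.
- **That the ICER will be biased or wrong.** Randomisation keeps the simple QALY and cost differences unbiased on average. The loss is precision and exposure to chance imbalance. Sampling error is something to quantify; neither adjustment nor a bootstrap corrects it.
- **That baseline imbalance passes straight into the QALY area.** The area as written begins at 3 months, so the route is indirect.
- **That the input-parameter step excludes sampling error.** The wording is vague and could be meant to cover a probabilistic analysis.
- **That the 2-year analysis will lack data.** SAP 3.1 reports that 2-year questionnaires, including EQ-5D-5L and RAND36, were collected, and the protocol's version history records a funding extension. Completeness is not stated, so the two protocol sentences still disagree, but the practical worry is much reduced.

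An acceptability curve and the choice of base-case horizon are reporting preferences, not defects.

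**Conclusion.** The point holds as a free improvement. Protocol 11.3 specifies neither baseline-utility adjustment nor patient-level sampling uncertainty for the ICER, and nothing else in the two documents supplies them. Followed as written, the analysis remains unbiased but gives up a 16% to 36% reduction in QALY variance. It also leaves in about 0.004 to 0.009 QALY per year for each one-SE baseline imbalance.

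Those sizes rest on an assumed SD of 0.10 to 0.15, equal SDs and r of 0.4 to 0.6; only the 182 per arm comes from the documents. Whether the shift matters for the decision depends on the true QALY and cost differences, which cannot be judged here.

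**What to change.** In 11.3 or the separate economic plan, before any unblinded economic analysis:

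1. Estimate incremental QALYs by regression on arm, baseline utility (same instrument) and site, and incremental costs by regression on arm and site. State the QALY window for each horizon, since the shift scales with it.
2. Report a bootstrap 95% interval for the joint cost-QALY result beside the ICER, resampling men with their costs and QALYs together. Incremental net benefit is one suitable form, because it avoids the unstable ratio when the QALY difference is near zero.
3. Reconcile the statement in 11.3 on follow-up for all men with the funding condition in 7.4, and report how complete the 2-year data are.

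Cost: a few lines of text and slightly more analysis. No new data are needed, because baseline EQ-5D-5L and RAND36 are already scheduled.

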## 11.4 Electronic Patient Reported Outcome Measures (e-PROMs)

As a further COVID-19 mitigation strategy, PROM questionnaires will be sent out electronically over email. Clinical research teams at each site will be able to send patients a personalised hyperlink to their NRS number (their trial number) to input their questionnaire answers onto our database. Patients will only have access to their specific NRS profile and for that visit's questionnaires only. These questionnaires contain no patient identifiable data and email addresses for these patients are not stored on the database. Data collected from the patients will be stored using the same company we currently use on a server that conforms to all data protection and HRA requirements. The database will contain no patient

identifiable data and will not be shared with anyone outside of the direct trial management team.

To ease patient burden and for those who may not want to use a computer, hardcopy CRFs can be sent in the post to be filled out and returned. They will then subsequently be entered onto the NeuroSAFE database by the trial team.

## 12 STATISTICS

### 12.1 Sample size

As of protocol version 5.0, the NeuroSAFE sample size justification has been updated based on the analysis of 50 patients included in the NeuroSAFE PROOF Feasibility Trial, which was relevant to the original version of this protocol. 25 men were randomly allocated to NeuroSAFE RARP and 25 allocated to standard RARP. They were then followed up to 12-months following treatment. Outcomes related to these men will not be included in main trial analysis.

Based on analysis of the feasibility trial outcomes, the primary outcome was defined as a comparison of erectile function recovery at 12-months between men who underwent NeuroSAFE RARP (intervention) vs. standard RARP (control) with recovery defined as an IIEF-5 score of 21 or above.

The previous recruitment target according to protocol version 4.0 (August 2019) was for 404 men (364 evaluable). This sample size was calculated without the benefit of mature functional (i.e. PROMs/IIEF-15) results related to erectile function recovery.

A new sample size using the newly informed outcome data from the feasibility trial was prepared for protocol 5.0. The sample size is based on a 14% higher proportion of men with IIEF-5 score of 21 and above in the NeuroSAFE RARP (intervention) arm, compared to the control baseline proportion. At 90% power, an alpha of 0.05 and a loss to follow up of 10%, 416 patients (374 evaluable) would be the anticipated recruitment target. This sample size calculation is therefore deemed to be compatible with the sample size calculation submitted and used within protocol version 4.0 (August 2019). Furthermore, the iDMC reviewed the sample size assumptions on 16th Feb 2021 and were unblinded to results from the first 150 men recruited to the main trial. They advised the trial continue recruitment to the original number of 404 men (364 evaluable men). The iDMC will continue to review the recruitment target during the trial.

The secondary outcome #1, the proportion of men regaining continence at 3 months as defined by ICIQ score of 5 or less, is powered at 89% for a 15% increase in the NeuroSAFE RARP (intervention) arm compared to the standard RARP (control) arm at 3 months.

Results of the feasibility trial used for sample size calculation have been redacted from this protocol document, as these are anticipated to be similar to interim results for the full powered ongoing trial, due to the internal design of feasibility trial which shared the same methods and centres as the main trial. The intention of restricted access to these preliminary results, is that these results should not influence recruitment to the main trial, because the feasibility trial was not powered to provide estimates of the primary or secondary outcomes. Full unblinded results

needed for sample size calculation are available in confidence for research ethics review and iDMC.

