### 12.2.4 Statistical methods

Primary outcome: Comparison of the unpaired proportions of men who recover erectile function at 12 months allocated to the NeuroSAFE intervention versus the control arm, based on an IIEF-5 score of 21 or more. Statistical significance will be established using 95% confidence intervals calculated using the Wilson method. P-values will be reported. Further planned subgroup and sensitivity analyses will be conducted as detailed in section 7.2.1

The secondary outcome #1 will use similar methods to the primary outcome.

There will be no adjustment of p-values for secondary outcomes for multiple testing. STATA statistical software will be used.

Due to interruption the trial due to COVID pandemic, collection of outcomes at particular time points has been affected, with 3- and 6-month time points being less regimented than anticipated. Prior to data lock, the statistical methods will be

reviewed. It is possible that analysis could use survival analysis of time to event analysis up to 12 months for both analyses, if that would make better use of data from multiple time points.

Statistical methods will be reviewed on analysis of a sample of 20% of all data prior to data lock, after data collection and cleaning.

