1.3 Trial diagram

1.4 Sample size

The sample size was based on detecting a 14% difference in the proportion of patients with an IIEF-5 score of 21 or above between the intervention (NeuroSAFE RARP) and control (standard RARP) groups (42% vs. 28%). 364 evaluable participants are required to have 80% power to detect such difference, with a two-sided alpha of 5%. Allowing for 10% drop out, the trial aimed to recruit 404 participants (202 per arm).

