4.7 Primary outcome analysis

The primary estimand of interest will be the difference in mean IIEF-5 score at 12 months between participants allocated to the NeuroSAFE and those allocated to the standard treatment group among those who received the surgery.

The primary outcome (the IIEF-5 score at 12 month) will be analysed using a normal linear regression model. The model will include randomisation group, site (the stratification variable), age, and IIEF-5 at baseline. Continuous covariates (age and IIEF-5) will be included as a linear term, while site will be included as categorical. The estimated coefficient for the adjusted mean difference between randomisation groups will be presented alongside its 95% confidence interval and two-sided p-value

The primary analysis will include everyone in the mITT population with IIEF-5 available at 12 months.

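### Protocol 12.1 states 90% power and SAP 1.4 states 80% for the same 14-point difference at almost the same sample size; with two-sided tests, no single control rate gives both

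*Protocol*

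**What the plan says.** Protocol 12.1 describes a version 5.0 recalculation built on a gain of 14 percentage points for NeuroSAFE in the share of men scoring at least 21 on the IIEF-5. It states: "At 90% power, an alpha of 0.05 and a loss to follow up of 10%, 416 patients (374 evaluable"). It compares this with the version 4.0 target of 404 men (364 evaluable) and concludes: "This sample size calculation is therefore deemed to be compatible with the sample size calculation submitted and used within protocol version 4.0 (August 2019"). It then records that the data monitoring committee "advised the trial continue recruitment to the original number of 404 men (364 evaluable men"). The control rate behind the calculation is deliberately withheld: "Results of the feasibility trial used for sample size calculation have been redacted from this protocol document".

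SAP 1.4 uses the same endpoint and the same 14-point difference, and prints the rates as 42% with NeuroSAFE and 28% with standard surgery. It says "364 evaluable participants are required to have 80% power to detect such difference, with a two-sided alpha of 5"%, and allows 10% dropout to reach 404.

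SAP 4.7 then defines a different primary analysis: "The primary estimand of interest will be the difference in mean IIEF-5 score at 12 months".

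**The concern.** The two sample-size sections describe one comparison in one trial, yet one implies a type II error of 10% and the other 20%. The evaluable numbers differ by only 10 men (374 against 364), far too few to account for the gap. Both are operative text, not an amendment history, and neither mentions the other's figure.

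The stated power matters most if the result is null, because readers will then ask how likely the trial was to miss a 14-point difference. The protocol also uses its calculation to support keeping 404 men. At the only control rate the documents show, 404 men give about 80% power, not about 90%. Finally, no power is stated anywhere for the mean-difference analysis that the SAP makes primary.

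**Working it through.** **Inputs**
- 14-point absolute difference in IIEF-5 of 21 or more (Protocol 12.1, SAP 1.4); 1:1 allocation (Protocol 7.1).
- Protocol 12.1: 90% power, alpha 0.05, 374 evaluable, 416 recruited, control rate withheld.
- SAP 1.4: 28% versus 42%, 80% power, two-sided 5%, 364 evaluable, 404 recruited.
- Sidedness is not given in Protocol 12.1. It is read as two-sided because Protocol 12.2.4 says: "Statistical significance will be established using 95% confidence intervals calculated using the Wilson method".

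**Formula** (pooled null variance, n per arm, p̄ the mean of the two rates):

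n = [z(1−α/2)·√(2p̄(1−p̄)) + z(power)·√(p1(1−p1) + p2(1−p2))]² / (p2 − p1)²

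**1. The SAP figure.** At 28% versus 42%, p̄ = 0.35, √(2×0.35×0.65) = 0.6745, and √(0.28×0.72 + 0.42×0.58) = 0.6672.
- 80% power: (1.960×0.6745 + 0.842×0.6672)² / 0.0196 = 181.0, so 182 per arm and 364 in total. This matches the SAP.
- Dropout: 364/0.9 = 404.4, which agrees with 404. For the protocol, 374/0.9 = 415.6, which agrees with 416.

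**2. The protocol figure at the SAP's rates.**
- 90% power: (1.960×0.6745 + 1.282×0.6672)² / 0.0196 = 241.8, so 242 per arm, 484 evaluable, and 484/0.9 = 538 recruited.
- Power = Φ([0.14·√n − 1.960×0.6745] / 0.6672). With n = 182 per arm (364) it is 80.2%; with n = 187 per arm (374) it is 81.3%.
- With unpooled variance, power is 80.8% and 81.8%. With a continuity correction, about 390 are needed for 80% and 512 for 90%. Neither variant reconciles the two statements.
- Starting from 28%, 90% power is reached only for a difference of 16.2 points with 364 evaluable, or 16.0 points with 374.

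**3. Control rates at which the protocol figure is right.** Solving for 90% power at 374 with a 14-point difference gives 15.9% or 70.1%. Between these rates, power at 374 is below 90%, with a minimum of 77.5% at 43%.

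| Control vs NeuroSAFE | N for 80% | N for 90% | Power at 364 |
|---|---|---|---|
| 28% vs 42% | 364 | 484 | 80.2% |
| 16% vs 30% (70% vs 84% is identical by symmetry) | 282 | 376 | 89.1% |

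**4. Can one control rate give both?** Allowing 3% tolerance on N, 374 at 90% needs a control rate of 14.9–16.7% or 69.3–71.1%. For 364 at 80% it is 26.1–30.7% or 55.3–59.9%. These ranges do not overlap. At any control rate, going from 80% to 90% power raises N by about a third (484/364 = 1.33; 376/282 = 1.33). The stated sizes differ by 374/364 = 1.03. This argument does not depend on the withheld rate.

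**5. The mean-difference analysis.** A two-sample t test with 182 per arm, two-sided 5%, detects 0.294 SD at 80% power and 0.341 SD at 90%, before covariate adjustment. The documents give no SD for IIEF-5. If it is assumed to lie between 5 and 9 points, these are 1.5 to 2.7 points and 1.7 to 3.1 points.

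**The case against.** The strongest defence is that the protocol's control rate is withheld on purpose and may differ from 28%. Near 16% or 70% its 374 at 90% is correct, and 364 still gives about 89%, so its statement of compatibility with version 4.0 holds on its own terms. This stands, and it is why the point is a conflict between documents and not an error shown in the protocol. It does not remove the conflict. SAP 1.4 presents 28% versus 42% as the basis of the sample size, and nothing explains a second control rate.

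Sidedness is the next objection, since Protocol 12.1 does not say two-sided. With a one-sided 5% test, 374 at 90% corresponds to a control rate of about 24.6%, where the SAP's two-sided 80% needs about 344. With 3% tolerance on both figures there is a narrow overlap at about 26.1–26.2%, or about 21–25% if the SAP figure also used a continuity correction. None of this helps at the SAP's stated 28%, where one-sided 90% needs 394, although one-sided power at 374 is 88.6%. The protocol's 95% interval rule also points to two-sided.

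It is also true that both documents agree on the operative target of 404 (364 evaluable), that planned power does not enter the estimate, interval or p-value, and that SAP 1.4 already ties its 80% to the difference in proportions. These points limit the consequence. They leave two stated powers for one comparison, and none for the analysis that is now primary.

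**Conclusion.** The concern holds. With both tests two-sided and 14% read as an absolute difference, no control rate supports 90% power at 374 and 80% at 364. At the SAP's 28% versus 42%, the retained 364 evaluable gives 80.2%; the protocol's 90% would need 484 evaluable, 120 more. The documents do not show which control rate should govern, so the protocol figure cannot be called wrong in itself. It is wrong at the only control rate they disclose. Separately, neither power statement applies to the mean-difference primary analysis. The point should be fixed, but it affects reporting and not the conduct of the trial.

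**What to change.** Reconcile Protocol 12.1 and SAP 1.4 so that one power statement governs, with its sidedness stated.

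- If the SAP's 28% versus 42% and the target of 404 (364 evaluable) govern, state about 80% power and withdraw the 90% with 416 and the compatibility statement from Protocol 12.1. The protocol can refer to SAP 1.4 and leave its own redaction in place.
- If another control rate underlies the 90%, state it and explain why the SAP uses 28%.
- In either case, add to SAP 1.4 that the 80% concerns the binary comparison at 21 or more and not the mean-difference primary analysis, for which 364 evaluable detects about 0.29 SD at 80% power or 0.34 SD at 90%, before covariate adjustment.

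The cost is wording only. If the SAP's rates govern, the stated power falls from 90% to about 80%. Patients, recruitment target and analysis do not change.
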